13.11 Development Safety Update Reports

DSURs will be co-ordinated by OCTO and prepared in collaboration with the CI and submitted in parallel to the regulatory authority and responsible Research Ethics Committee within 60 days of the anniversary of the date of regulatory approval. A copy of each report will be provided to Celsion and the sponsor

13.12 Informing Investigators of new safety information

The trial office or the Chief Investigator will ensure that all investigators are kept informed in a timely manner, as new safety profile information becomes available. Investigators are responsible for briefing their study team and onward transmission to R&D office as appropriate.

14 PREGNANCY

Pregnancies (in a participant or partner) occurring whilst taking part in the trial or within 6 months of the intervention require expedited reporting.

A pregnancy form should be completed and faxed to the trial office within the same timelines as an SAE. All reported pregnancies should be followed and the outcome reported using the same form. If the outcome of the pregnancy meets any of the criteria for seriousness, it must also be reported as an SAE. Examples of pregnancy outcomes that are SAEs include reports of:

- congenital anomalies or developmental delay, in the foetus or the child.
- foetal death and spontaneous abortion.
- suspected adverse reactions in the neonate that are classified as serious

Women who become pregnant should be withdrawn from trial treatment immediately

The Trial Office will report all pregnancies and any pregnancy-related SAEs to Celsion.

15 DEFINING THE END OF TRIAL

For this study the end of the trial is defined as:

The last follow-up with the last patient

The sponsor and the Chief Investigator reserve the right to terminate the study earlier at any time. In terminating the study, they must ensure that adequate consideration is given to the protection of the participants' best interests.

16 STATISTICAL CONSIDERATIONS

16.1 Sample size and power

Evaluable participants will be recruited to either Part I or Part II of the study, up to a maximum of 28 evaluable participants overall. Non-evaluable participants will be replaced (section 6.1).

17 STATISTICAL ANALYSIS PLAN

A statistical analysis plan written adhering to the current OCTRU standard operating procedures will be signed off for this trial prior to analysis of primary or secondary aims.

17.1 Inclusion in analysis

All evaluable participants in both Part I and Part II will be included in the final analyses. All patients enrolled in the study, will be accounted for and included in the analyses. The number of patients who were not evaluable, who died or withdrew before treatment began will be recorded.

Variables will be analysed to determine whether the criteria for the study conduct are met. This will include a description of patients who did not meet all the eligibility criteria, an assessment of protocol violations and other data that impact on the general conduct of the study.

Baseline characteristics will be summarised for all enrolled patients. Patients who died or withdrew before treatment started or do not complete the required safety observations will be described and evaluated separately.

Treatment related toxicity will be tabulated by type, grade of toxicity, relatedness to trial treatment and the worst grade toxicity experienced

Evaluable for toxicity: All patients will be evaluable for toxicity from the time of their intervention using NCI CTCAE v 4.0 scoring.

Adverse events will be summarised by the number of patients experiencing each type of event. The grades and causality will be reported.

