¹⁰ During the Ultrasound Session feasibility of intervention is confirmed and a target tumour will be selected by ultrasound. Only one screening ultrasound is required.

¹¹ MRI includes the abdomen. Measurements made using the modified RECIST 1.1 criteria.

¹² Liver MRI includes the abdomen. The first Liver MRI/MR Spectroscopy following intervention can alternatively be performed on the same day as intervention, if intervention is in the morning. It should occur within 36 hours of the completion of intervention, and ideally within 24 hours where possible.

¹³ Liver pCT includes the abdomen. Measurements made using CHOI and the modified RECIST 1.1 criteria.

¹⁴ Three blood samples for pharmacokinetics in both Phases I and II (Pre-Treatment, Unreleased drug, Released drug).

¹⁵ Three biopsies in Part I (Pre-Treatment, Unreleased drug, Released drug), two biopsies in Part II (Released drug).

KEY DEFINITIONS

“Intervention” refers to attempted targeted release of ThermoDox® by mild hyperthermia using a focused ultrasound.

The “FUS-targeted tumour” or “target tumour” refers to the liver tumour treated with FUS following ThermoDox® delivery. This is in contrast to the RECIST definition, which defines target tumours as those measurable lesions which are followed through the patient’s treatment course.

A “non-FUS control tumour” refers to a liver tumour receiving ThermoDox® alone which has been selected for radiological follow-up and comparison with the target tumour.

The “desired range of mild hyperthermia” is used in the context of ThermoDox® release in this study and is defined as achieved bulk tissue temperature in the range of 41-47°C

“Optimal FUS exposure parameters” are defined as those combinations of settings on the HIFU device (power, duty cycle and transducer motion plan) which result in an adequate temperature rise to successfully release doxorubicin from the LTSls in the target tumour, without causing direct thermal tissue damage.

An “evaluable participant” is defined as a participant who has received FUS following delivery of ThermoDox® in Part I or II, and for whom it has been possible to evaluate the outcome of the intervention based on biopsy samples, or radiologically.

An “evaluable sample” is defined as a sample for which sufficient material was available for analysis and the analytical technique has provided quantifiable data.

ABBREVIATIONS

AE	Adverse Event
ADL	Activities of Daily Living
ADR	Adverse Drug Reaction

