5.2 Evaluations during the intervention (d-1 to d2)

Evaluations on day -1 (pre-Intervention day)

- Dose of oral dexamethasone given as pre-medication (section 5.5.2 & 9.3)
- Baseline scans (Usually on d-1 but may be performed from day -7 to day 1 provided before intervention):
 - Liver MRI/MR -Spectroscopy
 - Liver pCT

- Whole body FDG PET-CT

Evaluations on day 1 (intervention day)

- Confirm d-1 pre-medications were given.
- Day 1 pre-medications given
- Confirmatory portable ultrasound to confirm tumour location before patient anaesthetised
- General anaesthetic start and finish time
- Dose of ThermoDox® administered, start and finish time
- Start and finish time of final FUS exposure and FUS parameters
- Thermometry data (Part I only)
- Bloods samples for pharmacokinetics (Pre-Treatment, Unreleased and Released plasma samples)
- Biopsy samples for assay quantification \pm microscopy:
 - Part I: Pre-Treatment, Unreleased, Released
 - Part II: Released
- Adverse event monitoring

Evaluations on day 2 (recovery day)

- Physical exam
- Vital signs: Temperature, resting pulse and blood pressure (BP) after participant has been in a sitting position for at least five minutes
- Full Blood Count (FBC); including Haemoglobin (Hb), white blood cells (WBC) with differential count (neutrophils and lymphocytes), and platelets
- Biochemical profile; including sodium, potassium, calcium, phosphate, urea, creatinine
- Liver profile; including total protein, albumin, bilirubin, ALP, AST and/or ALT and LDH
- Post-treatment Liver MRI/MR-Spectroscopy (within 36 hours, and ideally within 24 hours, of intervention¹⁸)
- Adverse event monitoring

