5.3 Follow-up and end of study evaluations (within 60 days)

Follow-up 1: Day 15 (± 3 day tolerance)

Parts I & II:

- Full Blood Count (FBC); including Haemoglobin (Hb), white blood cells (WBC) with differential count (neutrophils and lymphocytes), and platelets
- Biochemical profile; including sodium, potassium, calcium, phosphate, urea, creatinine
- Liver profile; including total protein, albumin, bilirubin, ALP, AST and/or ALT and LDH
- Adverse event monitoring

Follow-up 2: Day 30 (+7 not <30)

Parts I & II:

- Adverse event monitoring
- Concomitant medication recording
- Full Blood Count (FBC); including Haemoglobin (Hb), white blood cells (WBC) with differential count (neutrophils and lymphocytes), and platelets
- Biochemical profile; including sodium, potassium, calcium, phosphate, urea, creatinine
- Liver profile; including total protein, albumin, bilirubin, ALP, AST and/or ALT and LDH

Follow-up Scans: From Day 12 - Day 60 post-intervention as defined in the summary of schedule events (one set of scans at 4 weeks follow-up, the other being flexibly timed in accordance with emerging radiological data from previous study participants)

Parts I & II:

- Maximum of two follow-up Liver MRI/MR-Spectroscopy scans
- Maximum of two follow-up Liver pCT scans
- Maximum of two follow-up whole body FDG PET-CT scans

¹⁸ The time of intervention is defined as the time at which the final FUS exposure is complete

If a participant is withdrawn from the study following the intervention, adverse event recording should continue for 30 days post-intervention. No other follow-up evaluations will be required.

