13 ASSESSMENT OF SAFETY

Adverse event monitoring starts at intervention (Day 1) until Day 30 follow-up visit (which may be scheduled 30 days +7 but not <30 post intervention).. The Investigator will monitor each patient for clinical and laboratory evidence of adverse events on a routine basis throughout the study. Should an Investigator become aware of any study drug or study procedure related SAEs following this period these must also be reported as stated below. All reportable AEs will be followed to a satisfactory conclusion. Any reportable AEs that are unresolved at the patient's last visit in the study are followed up by the Investigator for as long as medically indicated, but without further recording in the CRF.

All AEs reported to the trial office will be processed according to internal SOPs, this includes the reporting procedure and assessment of causality and expectedness for SAEs. The TARDOX trial office may request additional information for any AE as judged necessary.

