13.3 Determining adverse event causality

The Investigator will assess and classify the relationship of an AE to the trial IMP (ThermoDox®) as follows:

Classification	Relationship	Definition
Drug-related	Definitely related	
 Starts within a time related to the study drug administration and No obvious alternative medical explanation.
	Probably related	
 Starts within a time related to the study drug administration and Cannot be reasonably explained by known characteristics of the patient's clinical state.
	Possibly related	
 Starts within a time related to the study drug administration and A causal relationship between the study drug and the adverse event is at least a reasonable possibility.
Not drug related	Probably related not	
 The time association or the patient's clinical state is such that the study drug is not likely to have had an association with the observed effect.
	Definitely related not	
 The AE is definitely not associated with the study drug administered.

The Investigator must endeavour to obtain sufficient information to confirm the causality of the adverse event (i.e. relation to the study drug, focused ultrasound exposure, liver biopsy, other illness, progressive malignancy or other cause) and give their opinion of the causal relationship between each AE and study drug, FUS and/or biopsy procedure. This may require instituting supplementary investigations of significant AEs based on their clinical judgement of the likely causative factors and/or include seeking a further specialist opinion.

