13.9 Reporting Adverse Events on the CRF

All AEs, including Serious AEs must be recorded on the case report forms (CRF) for that patient. The information provided will include date of onset, event diagnosis (if known) or sign/symptom, severity, time course, duration and outcome and relationship of the AE to study drug. Any concomitant medications or other any therapy used to treat the event must be listed. The Investigator will provide an "other" cause for serious AEs considered to be unrelated to the study drug. The study site should ensure data entered into the CRF is consistent with the SAE report information where applicable. SAE forms should be sent to the trials office within 24 hours of the incident occurring.

Each separate AE episode must be recorded. For example, if an AE resolves completely or resolves to baseline and then recurs or worsens again, this must be recorded as a separate AE. For AEs to be considered intermittent, the events must be of similar nature and severity.

Serious Events reporting requirements

Subjects having adverse events will be monitored with relevant clinical assessments and laboratory tests as determined by the Investigator. All adverse events must be followed to satisfactory resolution or stabilization of the event(s) including the investigation for the likely causative factor. Any actions taken and follow-up results must be recorded in the subject's source documentation. Follow-up laboratory results should be filed with the subject's source documentation. For all adverse events which require the subject to be discontinued from the study, relevant clinical assessments and laboratory tests will be repeated, on at least a weekly basis, until final resolution or stabilisation of the event(s). All SAEs will be included in analysis and must be reported to Celsion, regardless of cause, and will be classified as per section 13.3.

Non Serious Events reporting requirements

All Adverse Events (AE) including Adverse Drug Reactions (ADR) occurring up to 30 days following the intervention must be recorded on the CRF. The investigator will decide if those events are related to the medicinal product (i.e. unrelated, unlikely, possible, probable, definitely and not assessable) and the decision will be recorded on the CRF. AE definitely not drug related (i.e. reported as unrelated) will not be considered as adverse drug reactions in toxicity analyses, but reported separately.

Terms and Grading of Events

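### Sections 13.3 and 13.9 rate relatedness on conflicting scales, and section 17.1 both keeps and sets apart participants with incomplete safety observations, so related-event counts and toxicity denominators are not fixed

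*Protocol*

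**What the plan says.** **Relatedness.** Protocol section 13.3 gives five levels for the study drug. Definitely, probably and possibly related form the drug-related class. Probably not and definitely not related form the other class, and the probably-not level is described by saying that "the study drug is not likely to have had an association with the observed effect". The text under that table also asks for an opinion on the drug, the FUS and the biopsy.

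Section 13.9, on non-serious events, lists six levels: unrelated, unlikely, possible, probable, definite and not assessable. It then states: "AE definitely not drug related (i.e. reported as unrelated) will not be considered as adverse drug reactions in toxicity analyses". For serious events the same section refers back to the scale in 13.3.

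Secondary endpoint 4 (synopsis, and Table 2 in section 3) is adverse events to 30 days deemed related to ThermoDox and, separately, to FUS.

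**Who is counted.** Section 17.1 includes all enrolled patients in the analyses and adds: "All patients will be evaluable for toxicity from the time of their intervention". It also says that patients who died or withdrew before treatment, or who "do not complete the required safety observations will be described and evaluated separately". It does not say which observations are required.

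**When counting starts.** Footnote 18 in section 5.3 reads: "The time of intervention is defined as the time at which the final FUS exposure is complete". Its marker sits on the scan line in section 5.2: "Post-treatment Liver MRI/MR-Spectroscopy (within 36 hours, and ideally within 24 hours, of intervention". Section 13 says: "Adverse event monitoring starts at intervention (Day 1) until Day 30 follow-up visit".

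**The concern.** Safety is a secondary objective here, and the result will be small counts over a small denominator. Two written rules leave those counts open.

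First, an event judged unlikely to be due to the drug is not drug related under 13.3 but stays in the toxicity analyses under 13.9. An event that cannot be assessed has no place in 13.3 at all. Two analysts following the protocol could report different numbers for endpoint 4.

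Second, participants with incomplete safety observations are unlikely to be a random subset. Section 6 names unacceptable toxicity, and adverse events requiring discontinuation, among the reasons for early withdrawal. If they move to a separate evaluation, the main table can lose the people in whom toxicity was worst.

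A lesser matter is that the phrase fixing the start of toxicity evaluation resembles the one defined in footnote 18, which invites a late starting point.

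**Working it through.** The protocol states no toxicity rate, so there is no figure to reproduce. The check sets the rules side by side, then illustrates size with assumed counts.

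**1. Two relatedness rules**

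| Rating | Section 13.3 | Section 13.9 |
|---|---|---|
| Definite, probable, possible | drug related | kept in toxicity analyses |
| Probably not / unlikely | not drug related | kept (only unrelated is removed) |
| Definitely not / unrelated | not drug related | removed, reported separately |
| Not assessable | no such level | kept, by implication |

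Count under 13.3 = definite + probable + possible. Count under 13.9 = the same three + unlikely + not assessable. The difference is the number of events rated unlikely or not assessable, which the protocol cannot tell us in advance.

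Section 13.1 defines an adverse drug reaction as a response for which causality is at least a reasonable possibility. That matches the cut-off in 13.3, not the one in 13.9. Because 13.9 sends serious events to the 13.3 scale and uses its own for non-serious events, one endpoint would also pool two scales. Neither scale is written for FUS, although endpoint 4b needs it, so borrowing either one brings the same ambiguity.

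**2. Two denominators**

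- Section 17.1: all enrolled are included, and all are evaluable for toxicity.
- Section 17.1: incomplete safety observations lead to separate evaluation.
- Section 5.3: after withdrawal following the intervention, adverse event recording continues for 30 days and nothing else is required.
- Table 2: the Grade 3 and 4 laboratory endpoint uses post-intervention blood tests that include Day 15.

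So a participant withdrawn for toxicity before Day 15 need not have those bloods. If they count among the required observations, this participant is incomplete under 17.1.

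Illustration. Inputs: N = 28, the maximum of evaluable participants (section 16.1); 5 affected, suggested by the 18.9% neutropenia in Table 7 (0.189 × 28 = 5.3). The printed 65 of 354 is 18.4%, and 0.184 × 28 = 5.2 also rounds to 5. The number set aside, d, is assumed, and all d are assumed to be affected. Rate = (5 − d)/(28 − d), with exact 95% intervals.

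| d | Rate | 95% CI |
|---|---|---|
| 0 | 5/28 = 17.9% | 6.1 to 36.9 |
| 1 | 4/27 = 14.8% | 4.2 to 33.7 |
| 2 | 3/26 = 11.5% | 2.4 to 30.2 |
| 3 | 2/25 = 8.0% | 1.0 to 26.0 |

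A rarer event can vanish. If 2 of 28 are affected (7.1%, 0.9 to 23.5) and both are set aside, the table shows 0/26 (upper limit 13.2%).

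**3. The starting point**

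Applied to 17.1, footnote 18 would put the 30-minute infusion, the FUS exposures and the first two Part I biopsies before the clock. Section 8.4 allows up to 4 hours from infusion start to the end of FUS. Against that, section 13 starts monitoring on Day 1, section 5.2 lists adverse event monitoring among the Day 1 evaluations, and section 13.1 ties adverse events to administration of the study drug. The Key Definitions say that the intervention "refers to attempted targeted release of ThermoDox® by mild hyperthermia using a focused ultrasound", which gives no clock time. The Part I Released biopsy follows the final FUS exposure, and so do the Part II biopsies (section 5.4.2), so they are inside the clock on either reading.

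**The case against.** The strongest reply is that nothing in the text removes anyone or anything from the rates. Separate evaluation does not mean exclusion, the sentence stands in a paragraph on baseline characteristics, and two other sentences in 17.1 include everyone. Adverse event recording continues after withdrawal. Toxicity will be tabulated by relatedness, so a reader can see each level. No toxicity threshold or stopping rule depends on the figures, and the safety population is commonly settled in the SAP.

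Much of this stands. A reader might infer that toxicity is counted only after the last FUS exposure, so that infusion and procedure events are lost. The documents do not support that: footnote 18 belongs to a scan window, no adverse event rule cites it, the safety sections point to Day 1 and drug administration, and some biopsies come after FUS in any case. A reader might also infer that drop-outs are definitely removed from the rates. The text permits that reading but does not state it.

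What does not stand is the appeal to the SAP. These are statements in the protocol that contradict each other, and a SAP following one would depart from the other. Tabulation by level helps, but endpoint 4 still needs a cut-off, and the serious and non-serious scales do not share their levels.

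**Conclusion.** Wrong as written, as an internal contradiction in two places. Endpoint 4 has two possible counts, which differ by the events rated unlikely or not assessable. The toxicity table has two possible denominators, which differ by the participants with incomplete safety observations. The starting point is a minor ambiguity in wording.

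The drop from 17.9% to 11.5% is an illustration, not a forecast. It assumes 28 treated, 5 affected and 2 affected participants set aside. Non-evaluable participants are replaced, so the number treated may exceed 28, and nothing in the protocol predicts how many will have incomplete observations. The intervals overlap widely. The point is therefore a definite correction to make before analysis, but not one that undermines the trial.

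**What to change.** - **Sections 13.3, 13.9 and the CRF:** use one relatedness scale for serious and non-serious events. Count definite, probable and possible as related, state how not-assessable events are handled, and record the rating separately for drug, FUS and biopsy. Section 13.3 already asks for the three opinions.
- **Section 17.1, participants:** keep everyone who started the ThermoDox infusion or a Day 1 study procedure in the main toxicity table, whether or not safety observations are complete. List the incomplete ones in addition, with the observations they lack, so that a missing blood test is not read as a normal one.
- **Section 17.1, timing:** state that toxicity counts from the first Day 1 study procedure or the infusion, in line with sections 13 and 13.1, and that footnote 18 applies to scan timing only. Starting at the Day -1 premedication is not needed.

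The cost is a few sentences and a small CRF change. Reported toxicity rates may be slightly higher.

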17.2 Subgroup analysis

No subgroup analyses are planned for the study.

